## 8. Trial Population

### 8.1. Recruitment and Screening

Participant recruitment will primarily use social media (Facebook) and internet advertisements. The study population may contain biases such as a younger audience and those “tech savvy” enough to wear a medical device for the duration of the study compared to the general population. These potential limitations will be considered in the study’s scope of generalizability. For screening, participants who are more likely to fit inclusion criteria could be correlated with other social determinants of health, which will also be in the study’s scope of generalizability. Where population demographic information deviates far from the general population expected this will be highlighted.

## 8.2. Eligibility

[figure not shown]
### Inclusion and Exclusion Criteria

**Table 1. Criteria for study participants**

Inclusion	Exclusion

 
1. Living in the United States
 
2. Aged 21 years or older
 
3. Able to provide documentation of +PCR or +antigen test for COVID-19 within the past 48 hours
 
4. Self-reports that comfortable and willing to wear the wearable device and interact with a tablet-based interface daily
 
5. Able to provide a next of kin/designated person who can be contacted in the event of hospitalization for follow up.
 
	
 
1. Under the age of 21
 
2. Received a positive test result more than 48 hours prior to contacting study staff or has a pending test for COVID-19
 
3. Cannot confirm a PCR or antigen positive test for COVID-19.
 
4. Is unable to read English
 
5. Is unwilling to wear the device 24 hours/day except for showering/bathing or interact with a tablet-based interface for daily questionnaire
 
6. Is unwilling or unable to provide baseline data required for entry into the study
 
7. Is unable to provide a next of kin/designated person who can be contacted in the event of hospitalization for follow-up
 
8. Heavy tattooing on both upper arms
 
9. Known atrial fibrillation (permanent or paroxysmal)
 
10. Has taken/is taking part in a COVID19 vaccine or treatment study
 

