2. Increase in pulse rate to more than 90 beats per minute for 60 minutes with minimal body movement (Current Health motion score < 2)
3. Increase in respiratory rate to more than 25 breaths per minute with minimal body movement (Current Health motion score < 2)

In these instances, participants will be contacted and asked the following two to three questions:

We cannot provide you with any medical advice but would like to ask you a few questions. First, have you experienced any new signs or symptoms including:

Shortness of breath  
Chest pain or pressure  
New or worsening cough  
Fever or feeling feverish  
Chills  
Headache  
Sore throat  
Muscle aches or joint pain  
Abdominal pain  
Diarrhea  
Nausea  
Other, please specify

If yes, to any symptom:

- Do you consider the symptom to be mild, moderate, or severe (worst ever)?

- Do you intend to seek medical care at an emergency room, urgent care, or hospital in the near future?
- If no:
- Has your device been working properly, or has it been damaged in any way?

Throughout the study, if a participant believes they have recovered from COVID-19 for any of the reasons listed below and tells the study team they will be resuming normal life and would like to exit the study, we will consider these participants fully compliant. COVID-19 recovery would be considered in any of the following situations:

1. Participant receives a follow-up COVID-19 PCR test that is negative
2. Participant was asymptomatic and isolated for 14 days without symptoms
3. Participant was symptomatic and onset of symptoms was at least 14 days prior with the last three days symptom free

Conversely, if a participant feels that they are experiencing severe symptoms related to SARS-CoV-2/COVID-19 that warrant a visit to the hospital or urgent care facility (which will be also evident by our questionnaire), the participant will be instructed to contact their healthcare provider, contact a nearby hospital to arrange for appropriate assessment, or call 911 if an emergency. We will not provide medical advice, or a real-time monitoring service, as this will likely bias the outcomes of the trial. This will be made explicitly clear to participants in the Informed Consent Form and process of consent. The outcome of that visit will be captured by a study team member.

A study participant will be considered fully adherent to study protocol if they:

- Wear the device for at least 20 hours a day, at least 6 days a week up to 30 days

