## Inclusion and Exclusion Criteria

**Table 1. Criteria for study participants**

Inclusion	Exclusion
1) Living in the United States (contiguous states) 2) Aged 21 years or older	1) Under the age of 21 2) Received a positive test result more than 48 hours prior to contacting study staff or has a pending test for COVID19
3) Able to provide documentation of +PCR or +antigen test for COVID-19 within the past 48 hours 4) Self-reports that comfortable and willing to wear the wearable device and interact with a tablet-based interface daily	5) Able to provide a next of kin/designated person who can be contacted in the event of hospitalization for follow up. 3) Cannot confirm a PCR or antigen positive test for COVID-19 4) Is unable to read English

- |   |  |
|---|--|
| 
5) Is unwilling to wear the device 24 hours/day except for showering/bathing or interact with a tablet-based interface for daily questionnaire
 
6) Is unwilling or unable to provide baseline data required for entry into the study
 
7) Is unable to provide a next of kin/designated person who can be
 | 
contacted in the event of hospitalization for follow-up
 
8) Heavy tattooing on both upper arms
 
9) Known atrial fibrillation (permanent or paroxysmal)
 
10) Has taken/is taking part in a COVID-19 vaccine or treatment trial
 |
|---|--|
- 

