# 5. Study Objectives and Endpoints and Hypotheses

## 5.1. Study Objectives, Endpoints, and Outcomes

The overall objective of this study is to train, develop, validate and release a digital biomarker-based algorithm that, in COVID-19 PCR or antigen positive participants, within 30 days of a positive test:

1. Primary Outcomes:
  - a. Predicts likelihood of requiring a stay in hospital of at least 24 hours
  - b. Predicts likelihood of recovery from COVID-19 defined as:
    - i. For asymptomatic participants: 14 days without symptoms following positive test
    - ii. For symptomatic: at least 14 days since onset of symptoms, with the last three days symptom free
2. Secondary Outcomes:
  - a. Predicts likelihood of being admitted to ICU for either non-invasive (CPAP, BiPAP, high flow nasal oxygen), invasive ventilation or vasopressor support.
  - b. Predicts likelihood of death.
3. Tertiary Outcomes: Successful delivery, setup, daily interface engagement, and compliance with wearing of the device

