### 7.3.2. Per Protocol Population

- All subjects who adhere to the major criteria in the protocol as defined by adherence of wearing the CH device for 20 hours a day, 6 days a week, answer tablet surveys at least 6 days a week, and return the CH wearable device kit and tablet.
- The adherent per protocol population will be used for BN training and testing.

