## 8.4. Withdrawal and Follow-up

Participants may withdrawal at any time from the study if they no longer wish to wear the CH device and not respond to tablet based questions. The level of withdrawal, non-adherence, and loss of follow-up will be analyzed separately from modeling (7.3). Where possible CRA will capture reasons for withdrawal such as discomfort of continuous wear of device on upper arm. Withdrawal and loss of follow-up will be presented in the modified CONSORT flow diagram.

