#### Pilot

The pilot phase study with 50 participants will test the feasibility of recruitment, trial logistics, observed participant events, timeline to deterioration, and environmental test settings. The primary aim is to make any revisions to recruitment strategy and to the final number of “critical events” (e.g., hospitalization) required. The secondary aims are to produce descriptive statistics on pilot data, understand user issues that could affect study data, and begin formulating the structure of the Bayesian network. Descriptive statistics will include univariate analysis such as frequency, box plots, or histograms, and where appropriate, bivariate analysis on covariates using methods such as regression, Fisher’s exact tests, or chi-squared analyses.

#### Stage 1

The overall aim of Stage 1 is to collect enough data to perform machine learning analytics on data from the Current Health device to create a Bayesian network algorithm that successfully predicts the risk/probability of no severe disease, hospitalization, ICU admission, and death following SARS-CoV2/COVID-19 infection. The outcomes are *not* mutually exclusive categories, and can be hierarchical, i.e., when a participant first goes to hospital and then is admitted to the ICU. Conversely, a participant at risk could experience death without ever being hospitalized. This will be accounted for by calculating probabilities of each outcome and compare the conditional probabilities analyzing the risk of ICU admission, given that hospitalization has already occurred. One thousand participants will be recruited for the training stage.

Once the Bayesian network model is constructed, to account for model variation, that is a model's parameters change depending on the data the model is being given, cross-validation will be performed to ensure model stability and reduce issues with overfitting. Cross validation will only be conducted in the training data, as any cross validation with testing data has been shown in instances not to aid overfitting issues.

## Stage 2

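### Hospitalization is the only stated trigger for contacting the designated person, so the plan names no outcome source for a participant who stops responding, and the resulting losses would depend on severity

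*Combined protocol and SAP*

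**What the plan says.** **Contact.** Inclusion 5, in Table 1 of the protocol and of SAP 8.2, is "Able to provide a next of kin/designated person who can be contacted in the event of hospitalization for follow up". Exclusion 7 mirrors it in both documents: it begins "Is unable to provide a next of kin/designated person who can be" and ends with the same hospitalization condition. SAP 3 defines abbreviations for next of kin and designated person, but no procedure in the available text uses them.

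**Outcomes.** SAP 5.1 lists as a secondary outcome "Predicts likelihood of death". The Stage 1 text, in the protocol and in SAP 9.2, says "Conversely, a participant at risk could experience death without ever being hospitalized".

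**Ascertainment.** SAP 6.6 schedules outcome verification from Day 1 to Day 30 and for 30 days after observation ends. SAP 9.1 gives this task to the CRA and allows the second 30 days when neither recovery nor death is established. Neither section says whom the CRA asks or what follows if nobody answers. The four outcome variables in SAP 9.1 take only Yes or No.

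**Analysis.** SAP 8.4 states: "The level of withdrawal, non-adherence, and loss of follow-up will be analyzed separately from modeling (7.3"). SAP 7.3.2 states: "The adherent per protocol population will be used for BN training and testing". Membership of that population requires device wear, survey completion and return of the kit.

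**The concern.** The designated person is the only informant other than the participant whom the documents name. The stated occasion for using that informant is an admission that staff already know about. Two kinds of severe case do not meet that condition: a participant who dies or collapses at home, and a participant admitted suddenly who is too ill to report it. In both, silence is itself a consequence of severity.

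If these participants leave the model data, the training and test sets tilt towards milder cases who could still communicate. Performance for death and for sudden deterioration would then be estimated on a selected sample. The test cohort would not reveal this, because it is filtered in the same way as the training cohort.

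**Working it through.** 1. **The plan's own figure.** Protocol Data Analysis and SAP 6.3 assume a 10% event rate in cohorts of 1,000: 1,000 × 0.10 = 100 events per cohort. This reproduces and is not disputed. No expected number of deaths is given, and no share of deaths outside hospital.

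2. **A participant who falls silent at home.** The three protocol triggers are thresholds on oxygen saturation, pulse rate and respiratory rate. Each needs a reading, so a device that has stopped transmitting raises none. When a trigger does fire, the protocol has staff contact the participant, not the designated person. The daily survey goes unanswered and the CRA's adherence check gets no reply. No hospitalization is known, so the stated condition for contacting the designated person is not met. SAP 6.6 and 9.1 still require the CRA to verify the outcome but name no source. The written procedure ends there.

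3. **An abrupt admission.** The documented signals of an admission are the daily survey item on planning to go to hospital, the answers to a trigger call, and the participant's own report of severe symptoms. All come from the participant. If none is given, the contact condition presupposes the fact it is meant to establish.

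4. **What happens in the modelling.** SAP 7.3 gives an example of a participant hospitalized after 7 days, who counts as adherent with 7 × 20 = 140 hours of wear and 6 surveys.
   - Take the same participant with the admission unknown and adherence judged over the full 30 days. The minimum is 30 × 20 = 600 hours and 26 surveys.
   - By day 7 the most anyone can have is 7 × 24 = 168 hours and 7 surveys, so the participant fails.
   - The SAP does not say which period applies to a silent participant. With a shorter period there is still no outcome to model: SAP 8.4 sets loss to follow-up apart, and SAP 8.5 describes an analysis population that reached a study outcome.
   - With no value for unknown in SAP 9.1, the remaining option is to code No, which would be wrong for a true event.
   - Separately, a participant whose death at home is ascertained but whose kit is not returned fails the kit condition in SAP 7.3.2, and so is excluded even though the outcome is known.

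5. **Size for death (assumptions, not figures from the documents).** Take mortality of 0.5% to 2% and 5% to 30% of deaths outside hospital.
   - Low end: 1,000 × 0.005 = 5 deaths; 5 × 0.05 = 0.25 outside hospital.
   - High end: 1,000 × 0.02 = 20 deaths; 20 × 0.30 = 6 outside hospital.

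6. **Size for hospitalization.** A death at home is not a stay of at least 24 hours, so it removes none of the 100 events. An unannounced admission that is never learned of removes 1/100 = 1%, and five would remove 5/100 = 5%. The documents give no rate for such admissions.

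**The case against.** The line in Table 1 is an enrolment criterion. A reader might infer that the designated person may be contacted only on hospitalization. The criterion does not say so, and nothing in the text forbids other contact. A reader might also infer that the plan expects deaths at home, but it says only that they could occur.

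The tempting further step is that a silent participant is simply filed as lost to follow-up. No section says that. SAP 6.6 lists adherence checks throughout the 30 days, and the extra 30 days in SAP 9.1 are meant for participants with neither recovery nor death established. Many admissions would also be announced beforehand through the survey or a trigger call, and the protocol says staff will capture the outcome of a hospital or urgent care visit. Finally, the consent form and the text of SAP 1.4 (roles and responsibilities) were not available for this review. Either may give wider permission or a fuller procedure.

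All of this stands, and it limits the point. It does not remove it. The verification rows supply a person and a time window but no informant, and a longer window does not help if the participant cannot answer. Wider consent would permit a call, but the analysis plan would still need to say when the call is made and how its result is recorded. Unannounced admissions are only a part of all admissions, but they are the part for which the written contact condition cannot work.

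**Conclusion.** The point holds in limited form. Hospitalization is the only stated trigger for contacting the designated person, and the available text names no outcome source for a participant who stops responding. Followed as written, the plan can lose severe cases from training and testing because they are severe.

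The size is unknown. On the assumed ranges above, between 0.25 and 6 deaths per cohort would depend on the unwritten route; the low end is below one, while the high end is 6 of 20. These are deaths at risk of being missed, not a forecast of deaths lost. The effect falls mainly on the sparse death outcome and on unannounced admissions.

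A reader might conclude that home deaths erode the 100 planned hospitalization events, or that deaths are shown to be systematically lost. The documents support neither: the first confuses two outcomes, and the second needs rates and a filing rule that are not given. The change is still worth making, because the bias has a clear direction and the remedy is small.

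**What to change.** Three linked changes are needed. Rewording the contact criterion alone would not be enough, because the kit condition would still remove known deaths.

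- **Table 1, inclusion 5 and exclusion 7, in both documents:** state that the designated person may be contacted on hospitalization or on loss of contact. Change the consent wording too if it is equally narrow.
- **SAP 6.6 and 9.1:** state that when wearable signal and daily survey are both absent and the participant does not answer the adherence check, the CRA contacts the designated person and records alive, hospitalized, ICU, dead or unknown. State in SAP 8.4 that a participant is labelled lost to follow-up only after this contact has failed.
- **SAP 7.3.2:** count adherence up to the outcome date, as the example in SAP 7.3 already does for hospitalization. Do not exclude a participant with an ascertained hospitalization, ICU admission or death because the kit was not returned.

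This is a rule for ascertaining outcomes and does not change anyone's care. It costs wording in two tables and a few SAP sections, possibly a consent amendment, and a small number of calls by CRAs who already run adherence checks. Some calls will find only a device that was not being worn.

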### 8.3. CONSORT flow diagram

A CONSORT diagram modified for the observational design of the trial will be outlined as follows. Upon study completion each n= will be provided and reasons for ineligibility and loss of follow-up will be noted.

## 8.4. Withdrawal and Follow-up

Participants may withdrawal at any time from the study if they no longer wish to wear the CH device and not respond to tablet based questions. The level of withdrawal, non-adherence, and loss of follow-up will be analyzed separately from modeling (7.3). Where possible CRA will capture reasons for withdrawal such as discomfort of continuous wear of device on upper arm. Withdrawal and loss of follow-up will be presented in the modified CONSORT flow diagram.

## 8.5. Baseline Participant Characteristics

Characteristics will be presented in a descriptive summary table — continuous variables as mean and standard deviation or median and quartiles, and categorical and binary variables as absolute and relative frequencies. The analysis population will be produced for those who complete the trial to a study outcome including recovery. Surveys will be administered via tablet, which is part of the CH device kit a participant receives. The list of baseline participant characteristics and description of how they will be recorded are captured in the following table. The variables planned to be captured represent the most recent literature findings of COVID-19 risk factors.

Description	Variable	Variable Type
*Participant Intake Survey		
Date of birth	dob	Date (MMDDYYYY)
Sex	sex	Categorical: Male, Female, Other or prefer not to specify
Pregnant	pregnant	Binary: Yes, No
Presence of menstrual periods	menstrual_periods	Binary: Yes, No
Absence of menstrual periods reason	no_periods_reason	Categorical: Pregnant or breastfeeding, Taking hormonal birth control, Undergoing menopause or post-menopausal, High active, Other
Date of last period	last_period	Date (MMDDYYYY)
Occupational category	occupational_cat	Categorical: Healthcare, Service industry, Retail, Office - able to work from home, Office - unable to work from home, Currently unemployed, Student - remote, Student - attending class in person
Household make-up	household_makeup	Binary: Living alone, Living with people
Do other members of your household currently have COVID-19?	household_covid	Binary: Yes, No

Are any other members of your household enrolled in Current Health's COVID-19 study?	household_study	Binary: Yes, No
What is your self-identified race/ethnicity?	race_ethnicity	Categorical: White Hispanic, White Non-Hispanic, Black or African American, Asian, American Indian or Alaska Native, Native Hawaiian and Pacific Islander
Height	height	Discrete (user input)
Weight (in pounds)	weight	Continuous: (pounds or kg user input)
Asthma	asthma	Binary: Yes, No
Cancer	cancer	Binary: Yes, No
Chronic obstructive pulmonary disease (COPD)	copd	Binary: Yes, No
Diabetes	diabetes	Binary: Yes, No
Heart condition	heart_condition	Binary: Yes, No
High blood pressure	hbp	Binary: Yes, No
Kidney disease or reduced kidney function	kidney_disease	Binary: Yes, No
Organ transplant	organ_transplant	Binary: Yes, No
Sickle cell disease	sickle_cell_disease	Binary: Yes, No
Smoker	smoker	Binary: Yes, No
Intake survey feedback	intake_survey_feedbackk	Long free text
†Daily Survey		
Loss of smell or taste	loss_smell_taste	Binary: Yes, No
Is your loss of smell or taste better or worse than yesterday?	loss_smell_taste_likert	Categorical: Much worse, Worse, The same, Better, Much better
Dry cough	dry_cough	Binary: Yes, No
Is your dry cough better or worse than yesterday?	dry_cough_likert	Categorical: Much worse, Worse, The same, Better, Much better
Sore throat	sore_throat	Binary: Yes, No
Is your sore throat better or worse than yesterday?	sore_throat_likert	Categorical: Much worse, Worse, The same, Better, Much better
Fever or feeling feverish	fever	Binary: Yes, No
Is your fever better or worse than yesterday?	fever_likert	Categorical: Much worse, Worse, The same, Better, Much better
Chills	chills	Binary: Yes, No

Are your chills better or worse than yesterday?	chills_likert	Categorical: Much worse, Worse, The same, Better, Much better
Muscle aches	muscle_aches	Binary: Yes, No
Are your muscle aches better or worse than yesterday?	muscle_aches_likert	Categorical: Much worse, Worse, The same, Better, Much better
Diarrhea	diarrhea	Binary: Yes, No
Is your diarrhea better or worse than yesterday?	diarrhea_likert	Categorical: Much worse, Worse, The same, Better, Much better
Nausea	nausea	Binary: Yes, No
Is your nausea better or worse than yesterday?	nausea_likert	Categorical: Much worse, Worse, The same, Better, Much better
Are there any other symptoms or differences in health you would like to report?	daily_survey_feedback	Long free text
Will you speak to a healthcare provider due to worsening symptoms today?	self_reported_provider_care	Categorical: Yes, No, Maybe
Will you go to the hospital due to worsening symptoms today?	self_reported_hospital	Categorical: Yes, No, Maybe
Do you feel as though you have completely recovered from COVID-19 as of today?	self_reported_recovery	Categorical: Yes, No, Maybe

\*Participant Intake Survey questions are to be completed by participant one time.

†Daily Survey questions are asked once a day at the same time each day.

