## Research Objective and Outcomes

The overall objective of this contract is to train, develop, validate and release a digital biomarker-based algorithm that, in COVID-19 PCR or antigen positive patients, within 30 days of a positive test:

1. **Primary Outcome:** predicts likelihood of requiring a stay in hospital of 24 hours or longer
2. **Secondary Outcomes:**
  - a. Predicts likelihood of being admitted to ICU for either non-invasive (CPAP, BiPAP, high flow nasal oxygen), invasive ventilation or vasopressor support.
  - b. Predicts likelihood of death.
3. **Tertiary Outcomes:** Provides successful delivery, setup, daily interface engagement, and compliance with wearing of the device

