### 7.3.1. Full Analysis Population

- All subjects who receive CH kit
- The participants will be represented in flow diagram and analyzed for where participants systematically dropped out or did not adhere to study protocol. Participant feedback will also be captured and analyzed on this population.

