## 9. Analysis

### 9.1. Outcome definitions

Study outcomes will be ascertained by the CRA within the study observational period of 30 days or the following 30 days if the participant has not definitively experienced other outcomes of recovery or death.

Primary and secondary outcomes are presented in (5.1) and will be presented as follows.

Description	Variable	Variable Type
Recovery from COVID-19	recovered	Binary: Yes, No
Hospital stay of 24 hours or longer	hospitalized	Binary: Yes, No
ICU admission	icu_admission	Binary: Yes, No
Death	death	Binary: Yes, No

No calculations are necessary to derive primary or secondary outcomes, they all will be directly stated in binary terms.

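### SAP 8.5 and 7.3.2 define different analysis populations; if 8.5 governs modeling, unresolved but never-hospitalized participants drop out, which can bias the AUC

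*Combined protocol and SAP*

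**What the plan says.** Three places in the SAP bear on who is analyzed.

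- Section 7.3.1 defines the full analysis population as "All subjects who receive CH kit" and uses it for the flow diagram, dropout and participant feedback.
- Section 7.3.2 defines the per-protocol population by wear time, survey completion and kit return, and adds: "The adherent per protocol population will be used for BN training and testing".
- Section 8.5, on baseline characteristics, says: "The analysis population will be produced for those who complete the trial to a study outcome including recovery".

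The first primary outcome in SAP 5.1 is "Predicts likelihood of requiring a stay in hospital of at least 24 hours", counted "within 30 days of a positive test". The protocol's objectives section gives the same target: "predicts likelihood of requiring a stay in hospital of 24 hours or longer". SAP 5.2 attaches the 75% acceptance criterion to hospitalization only.

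The second primary outcome in SAP 5.1 is recovery. For symptomatic people it requires "at least 14 days since onset of symptoms, with the last three days symptom free".

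SAP 9.1 codes recovery, hospital stay, ICU admission and death as separate Yes/No variables. It lets ascertainment run into "the following 30 days if the participant has not definitively experienced other outcomes of recovery or death".

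**The concern.** Take an adherent participant who is followed throughout, returns the kit, is never admitted, and still reports a listed symptom such as cough or loss of smell at the end of ascertainment. That person never has three symptom-free days, so recovery is No. Hospital stay, ICU admission and death are also No. Read literally, 8.5 leaves the person out; read alone, 7.3.2 keeps the person in.

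For hospitalization nothing is missing: the person is a verified non-event. Excluding such people means that non-events enter only by recovering, a fact learned after the predictions are made. The model is meant for everyone who tests positive, and at that point nobody knows who will recover promptly. What is at stake is the AUC, PPV and event rate behind the deployment rule in SAP 5.2 and 6.4, and whether recovery is scored as an outcome distinct from hospitalization.

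**Working it through.** **Step 1. Who is in each set.** All rows assume an adherent participant with verified outcomes.

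| Participant | 7.3.2 | 8.5, literal | hospitalized | recovered |
|---|---|---|---|---|
| Hospital stay of 24 hours or more | in | in | Yes | Yes or No |
| Never admitted, recovery criteria met | in | in | No | Yes |
| Never admitted, died | in | in | No | No |
| Never admitted, alive, unresolved after the 9.1 extension | in | out | No | No |

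The sets differ only in the last row. With that row removed, every never-admitted survivor has recovered = Yes. Recovered = No can then occur only among people with a hospital stay, ICU admission or death. Admitted people may still recover, so 1b is not an exact mirror of 1a, but it carries little separate information.

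**Step 2. Event rate.** The SAP's figure reproduces: 1,000 × 0.10 = 100 events, leaving 900 non-events per cohort. The documents give no unresolved share, so let f be the assumed share of non-events that is unresolved. After the exclusion the event rate is 100 / (100 + 900(1 − f)): 10.2%, 10.5%, 11.0% and 12.2% for f = 2%, 5%, 10% and 20%.

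**Step 3. AUC.** The AUC averages over non-events:

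full AUC = (1 − f) × AUC against recovered + f × AUC against unresolved.

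Dropping the unresolved leaves only the AUC against recovered. To link the two terms, assume unit-variance normal scores with mean 0 for recovered non-events, d for cases and r·d for unresolved non-events. Then AUC against recovered = Φ(d/√2) and AUC against unresolved = Φ((1 − r)d/√2). Choose d so that the full AUC is 0.75. Both f and r are assumptions. At r = 0 unresolved people score like recovered ones, at r = 1 like cases, and at negative r lower than recovered ones.

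Worked cases:
- f = 10%, r = 1: 0.75 = 0.9x + 0.1 × 0.5, so x = 0.70/0.90 = 0.778.
- f = 20%, r = 1: x = (0.75 − 0.10)/0.80 = 0.8125.
- f = 10%, r = 0.5: d = 1.009 gives 0.9 × 0.7623 + 0.1 × 0.6394 = 0.750, so the AUC after exclusion is 0.762.

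AUC after exclusion when the full AUC is 0.75:

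| f | r = −0.25 | r = 0 | r = 0.5 | r = 1 |
|---|---|---|---|---|
| 2% | 0.749 | 0.750 | 0.752 | 0.755 |
| 5% | 0.748 | 0.750 | 0.756 | 0.763 |
| 10% | 0.745 | 0.750 | 0.762 | 0.778 |
| 20% | 0.740 | 0.750 | 0.776 | 0.813 |

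**Step 4. Against sampling error.** The Hanley-McNeil standard error for AUC 0.75 with 100 events and 900 non-events is about 0.029. Shifts at 2% to 5% unresolved are below half of that. The deployment rule asks for an AUC significantly above 0.75 at the 0.05 level, with sidedness not stated. The observed value must therefore reach about 0.75 + 1.645 × 0.029 = 0.798 one-sided, or 0.75 + 1.96 × 0.029 = 0.807 two-sided. With a true AUC of exactly 0.75 and a one-sided test, the chance of passing is 5% without the exclusion. At f = 10% it becomes about 11% for r = 0.5, since (0.798 − 0.762)/0.029 is about 1.2, and 24% for r = 1. At f = 20% it is about 22% and 69%.

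**The case against.** The case against is substantial.

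- **Section 7.3.2 already names the modeling set.** The 8.5 sentence sits under baseline characteristics and mentions no model. A reader might infer that the SAP definitely removes unresolved people from the AUC. The documents do not support that; it is one possible reading. The conflict remains, because the two rules can be applied together, 8.5 speaks of the analysis population without limiting it to a table, and nothing ranks one above the other. If only the baseline table was meant, that table could describe a different set from the one modeled.
- **The sentence may mean that an outcome was ascertained.** SAP 9.2 lists absence of severe disease among the Stage 1 targets, and 9.1 records hospitalization as Yes or No, so a never-admitted survivor arguably has an outcome. This would fit 8.4, which keeps withdrawal and loss to follow-up apart from modeling. It is a fair reading, but naming recovery as an included outcome points the other way, and the text does not decide it.
- **The 9.1 extension shrinks the group.** This stands. Only people unresolved after up to 30 further days are affected, so the larger shares above may be too high.
- **The direction of bias is assumed.** This also stands. Symptoms and vital signs are model inputs, so it is plausible that persistently symptomatic non-events score nearer to cases. Someone whose only remaining symptom is loss of smell may not.
- **The rule is not a bare 0.75.** A reader might infer that a reported 0.77 could trigger deployment wrongly. It could not: (0.77 − 0.75)/0.029 is about 0.7 standard errors. The observed AUC must be roughly 0.80, with reasonable sensitivity, specificity and calibration besides.

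**Conclusion.** The SAP gives two populations that differ in whether an outcome must be reached, and does not say which one produces the reported performance. That can be seen from the text without any numerical assumption. The same is true of the consequence for recovery, if 8.5 is applied to modeling.

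The effect on AUC is conditional. With a true AUC of 0.75 and unresolved people scoring between halfway to cases and level with them, it is about +0.002 to +0.013 at 2% to 5% unresolved and +0.012 to +0.063 at 10% to 20%. Under the same assumptions, a true AUC of 0.72 would read 0.731 to 0.775 at 10% to 20%, which can cross 0.75 as a point value but stays short of the significance threshold in expectation. If unresolved people score like recovered ones the shift is zero; if they score lower it is slightly negative, down to −0.010 in the range tried. It would be wrong to say that the AUC is inflated as a matter of fact. The supportable statement is that the plan permits an outcome-dependent exclusion in the set that may decide deployment, and that this can inflate AUC and PPV.

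The point covers only people whose hospitalization status is verified, not those lost to follow-up.

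**What to change.** State one modeling population and use it in both 7.3.2 and 8.5. For example:

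*For hospitalization, ICU admission and death, the modeling population is every participant otherwise eligible for modeling under 7.3.2 whose status for that outcome is verified at the end of the outcome window. Reaching recovery is not a condition of entry. Survivors who were never admitted and whose symptoms have not resolved are coded hospitalized = No and recovered = No. Recovery status is used only when recovery is the outcome being scored.*

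Three consistency edits go with it:

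- Define the outcome window once. SAP 5.1 counts 30 days from the positive test, 6.6 counts from kit arrival, and 9.1 allows 30 more days. State how an event found in the extension is coded.
- Keep 8.4 in line, so that withdrawal and loss to follow-up are handled as unknown status and are not confused with unresolved illness. Report the number in each group.
- If the 8.5 sentence was meant only for the baseline table, say so, and present that table for the modeling population.

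The cost is a short SAP edit, best made before Stage 2 testing. No new data are needed, since hospitalization status and symptoms are already collected. The reported AUC and PPV may come out slightly lower.
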